## 1 INTRODUCTION AND BACKGROUND INFORMATION

CAD-1883 is an investigational product being developed as a new treatment for Essential Tremor (ET), a movement disorder characterized by dysfunction of the cerebellum and its associated motor control circuit (Haubenberger et al, 2018). Tremor is defined as a rhythmic and oscillatory movement of a body part with a relatively constant frequency and variable amplitude. It is caused by alternating contractions of antagonistic muscles. Tremor is the most common of all movement disorders, and ET is the most common neurologic cause of tremor. The usual course of ET is one of gradual progression. Patients with persistent disability from ET need continuous symptomatic drug therapy. Available drug treatments are not effective in all patients, often provide inadequate symptomatic relief, and the symptomatic benefit of chronic administration often declines over time and is frequently associated with intolerable side effects. Therapy options for ET patients who do not benefit from pharmacologic treatment include deep brain stimulation (DBS) requiring surgery for placement of brain stimulator(s), magnetic resonance image (MRI)-guided thalamotomy via focused ultrasound (to treat persistently disabling unilateral limb tremor), or botulinum toxin injections (to treat persistently disabling hand, head, or vocal cord tremor). The efficacy of these invasive, non-pharmacologic therapies may also wane over time, and may be associated with intolerable side effects. Therefore, to address these important unmet medical needs, efforts are required to develop new treatments for ET targeting the cerebellar dysregulation responsible for the movement disorder.

The cerebellum is required for coordinated motion, including movements of the hands, limbs, trunk, and eyes, and the synchrony of speech, all of which are disrupted in ET. The cerebellar cortex, together with the inferior olivary nucleus and deep cerebellar nuclei, comprises the olivocerebellar circuit. Cerebellar output critically depends on the precise timing of action potentials in the principal neurons of the olivocerebellar circuit, especially cerebellar Purkinje neurons (Llinas, 2014).

Small conductance calcium-activated potassium (SK) channels are a family of potassium channels gated by intracellular calcium (Kshatri, 2018) In neurons, SK channels are gated by calcium that passes through voltage-gated calcium channels, which are activated by each action potential. SK channels regulate action potential timing by generating hyperpolarizing potassium currents between action potentials. In principle neurons of the olivocerebellar circuit, including cerebellar Purkinje neurons and their major afferent neurons of the inferior olivary nucleus, SK2 and SK3 channel-mediated after-hyperpolarizing currents represent a molecular pace-making mechanism centrally implicated in the coordination of movement.

Commercially Confidential Information

CAD-1883 is anticipated to be used for the treatment of ET throughout the course of the patient's disease. This study offers the opportunity to understand the safety, tolerability, and efficacy of CAD-1883 in the ET patient population.

### **1.1 Rationale and Risk Benefit**

The study will be open-label consisting of 1 treatment group receiving twice-daily oral dosing of CAD-1883 for a treatment period of 14 days.

Commercially Confidential Information

The selected dose is anticipated to be well-tolerated by subjects with ET for the duration of the treatment period. A 14-day treatment period represents an adequate time period to permit the initial assessment of safety and tolerability of CAD-1883 as well as a determination of early treatment effect on reducing the magnitude and severity of tremor while limiting the potential risk associated with a novel investigational drug.

## **2 STUDY OBJECTIVES**

### **2.1 Primary Objective(s)**

The primary objective of this study is to evaluate the safety and tolerability of twice-daily oral dosing of CAD-1883 over 14 days of treatment in adult patients with ET.

### **2.2 Secondary Objectives**

The secondary objectives of this study are to evaluate the efficacy of twice-daily oral dosing of CAD-1883 over 14 days of treatment as measured by:

- The Essential Tremor Rating Assessment Scale (TETRAS)-performance subscale (PS) total score change from Baseline to Day 14
- TETRAS-PS upper limb subscale score change from Baseline to Day 14

Commercially Confidential Information

- Change from Baseline to Day 14 in upper limb tremor severity, mean amplitude, and mean frequency, measured in the clinic using a wearable sensor

Commercially Confidential Information

## 3 STUDY DESIGN

### 3.1 Summary of Study Design

This is an open-label study designed to evaluate the safety, tolerability, and efficacy of CAD-1883 administered twice daily orally to adult subjects with ET.

Subjects will undergo a screening period of a minimum of 14 days up to a maximum of 35 days in which the subject will “wash-out” from prior tremorgenic and anti-tremor medications, to allow the effects of previous medication(s) on tremor to be eliminated. During the Screening period, each subject will undergo full assessment including medical and treatment history for ET, physical and neurological examination, in addition to laboratory testing, 12-lead electrocardiogram (ECG), and other screening assessments. The diagnosis of ET must be established by the Principal Investigator at Screening based on the Movement Disorder Society (MDS) criteria ([Bhatia, 2018](#)) with a documented severity of tremor based on the clinician-administered TETRAS-PS ([Elble, 2012](#)).

Commercially Confidential Information

Safety and tolerability will be monitored throughout the study duration including in-clinic assessments of adverse events (AEs), serious adverse events (SAEs), vital signs including orthostatic vital signs, 12-lead ECG, urinalysis, hematology, clinical chemistry, and CAD-1883 plasma concentration level on Days 1, 7, 14, and 21.

Efficacy will be evaluated as follows:

- TETRAS-PS total score change from Baseline to Day 14
- TETRAS-PS upper limb subscale score change from Baseline to Day 14

Commercially Confidential Information

- Change from Baseline to Day 14 in upper limb tremor severity, mean amplitude, and mean frequency, measured in the clinic using a wearable sensor

Commercially Confidential Information

The TETRAS-PS will be recorded via videography for centralized evaluation and rating by an independent blinded panel of expert(s).

At the Baseline/Pre-dose visit, subjects will undergo all required procedures including confirmation that all eligibility criteria are met.

The Day 1 visit can occur up to 3 business days following the Baseline/Pre-dose visit. Analysis of the pre-dose laboratory assessments (chemistry, hematology, urinalysis) should be conducted by the Central Laboratory, with the results available and reviewed by the Principal Investigator, or designee, prior to dosing the subject with CAD-1883 (Day 1 visit). On Day 1, subjects will be dosed in the clinic with the first dose of CAD-1883 300 mg (3 capsules of 100 mg each) and will

be monitored in the clinic prior to ingesting the second dose of CAD-1883 300 mg (3 capsules of 100 mg each), 4 to 5 hours later. Additional safety and all efficacy assessments will be completed after the 2nd in clinic dose on Day 1 as specified in the SOA ([Appendix A, Table 2](#)).

Subjects will be dispensed study drug for continued twice-daily oral self-administration at home. After Day 1, subjects are instructed to ingest the first daily dose of CAD-1883 of 300 mg (3 capsules of 100 mg each). The second daily dose of CAD-1883 300 mg (3 capsules of 100 mg each) will be taken 8 hours ( $\pm 2$  hours) after the first daily dose. Each subject is provided with a medication diary to denote the date and time of at-home study drug dosing.

The pre-dose laboratory assessments (chemistry, hematology, urinalysis) should be sent to the Central Laboratory for analysis. Under exceptional circumstances, the pre-dose laboratory assessments (chemistry, hematology, urinalysis) can be sent for expedited analysis at the local laboratory, along with duplicate samples sent to the Central Laboratory. The results of laboratory assessments should be available and reviewed by the Principal Investigator, or designee, prior to dosing the subject.

Additionally, a urine sample will be collected for determination of baseline levels of composite biomarker panel for renal tubular injury, which is not part of eligibility determination.

Subjects will return to the site for further assessments on Day 7 (-1 day) and Day 14 ( $\pm 1$  day) and the Follow-up visit (Day 21 [ $\pm 1$  day]).

On Days 1, 7, 14, and 21, subjects will undergo safety monitoring consisting of reporting of AEs or SAEs, collection of vital signs including orthostatic vital signs, undergo a 12-lead ECG, and collection of urine for urinalysis and a composite biomarker panel for renal tubular injury, and blood for hematology, clinical chemistry, and plasma drug level. On Day 1, 7 and 14, all urine and blood collections should take place after the TETRAS-PS assessment. Assessment of rating scales and upper limb wearable sensor measurements will also be performed.

On Day 7 and Day 14, the subjects are instructed to ingest the first daily dose of CAD-1883 of 300 mg (3 capsules of 100 mg each) at home 4 to 5 hours prior to the scheduled and/or anticipated dosing of the second daily dose of CAD-1883. The second daily dose of CAD-1883 300 mg (3 capsules of 100 mg each) will be taken in the clinic, under the supervision of study staff, 4 to 5 hours after the first daily dose.

Commercially Confidential Information

subjects will have the option to complete at-home assessments of tremor using the wearable sensor.

Commercially Confidential Information

Commercially Confidential Information

Upon completion of the 14-day treatment period, subjects will return to the site for the Day 21 Follow-up visit, approximately 7 days ( $\pm 1$  day) after the last dose of study drug was administered.

### **3.2 Study Indication**

CAD-1883 is an investigational product being developed as a new treatment for ET, a movement disorder characterized by dysfunction of the cerebellum and its associated motor control circuit ([Haubenberger et al, 2018](#)).

### **3.3 Study Endpoints**

#### **3.3.1 Primary Endpoints**

- The occurrence and severity of treatment emergent AEs.

#### **3.3.2 Secondary Endpoints**

- TETRAS-PS total score change from Baseline to Day 14
- TETRAS-PS upper limb subscale score change from Baseline to Day 14

Commercially Confidential Information

- Change from Baseline to Day 14 in upper limb tremor severity, mean amplitude, and mean frequency, measured in the clinic using a wearable sensor

Commercially Confidential Information

#### **3.3.3 Exploratory Endpoints**

Commercially Confidential Information

Commercially Confidential Information

## 4 SELECTION AND WITHDRAWAL OF SUBJECTS

### 4.1 Inclusion Criteria

Subjects who meet all of the following criteria will be eligible to participate in the study:

1. Adult subjects between 18 and 75 years of age, inclusive, with history of tremor that fulfills the diagnostic criteria of ET according to Movement Disorder Society (MDS) Consensus Statement on the classification of tremors from the task force on tremor of the International Parkinson and Movement Disorder Society ([Bhatia, 2018](#)).
2. Duration of ET illness since the first symptoms were noticeable of at least 3 years or more prior to screening, based on the subject's self-report, with onset prior to age 65 years old, per the Principal Investigator's assessment during screening.
3. Commercially Confidential Information

4. Commercially Confidential Information

5. Commercially Confidential Information
6. Except for ET, subjects must be otherwise healthy as determined by the Investigator, based upon a medical evaluation including medical history, physical examination, laboratory tests, and 12-lead ECG.
7. Subjects are able to understand study activities required, can give written informed consent, and are willing to comply with the requirements and restrictions of the study.
8. Women of childbearing potential must undertake a pregnancy test with documented negative **serum** pregnancy test at Screening and negative **urine** pregnancy test result at Baseline/Pre-dose, Days 7 and 14 before administration of the study drug, and then at the Follow-up visit (Day 21).
9. Postmenopausal women must have had  $\geq 365$  days of spontaneous amenorrhea, with documented follicle-stimulating hormone (FSH)  $\geq 38$  IU/mL, prior to screening. If needed, per Investigator's judgment, FSH level can be performed at Screening.
10. Surgically sterile women must have documentation of a hysterectomy, bilateral ovariectomy, or bilateral tubal ligation.
11. Female subjects with reproductive potential and male subjects with reproductive potential or who have female partners of reproductive potential, must agree to use two effective methods of contraception from signing informed consent until 90 days after the last dose of study drug. Acceptable forms of contraception include double barrier (i.e., condom with spermicide); surgically sterilized partner (180-day minimum); or abstinence.

12. Commercially Confidential Information

13. Commercially Confidential Information

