## 6 STUDY PROCEDURES

- Study procedures and their timing are summarized in the SOA ([Appendix A, Table 2](#)). Protocol waivers or exemptions are not allowed.
- Immediate safety concerns should be discussed with the Investigator, Medical Monitor, and Sponsor immediately upon occurrence or awareness to determine if the subject should continue or discontinue study intervention.
- Adherence to the study design requirements, including those specified in the SOA ([Appendix A, Table 2](#)), is essential and required for study conduct.
- All screening evaluations must be completed and reviewed to confirm that potential subjects meet all eligibility criteria. The Investigator will maintain a screening log to record details of all subjects screened and to confirm eligibility or record reasons for screening failure, as applicable. See [Section 6.1.1](#) for information about re-screening subjects.

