**Table 2: Schedule of Assessments**

ASSESSMENTS	SCREENING	BASELINE	TREATMENT								FOLLOW-UP
	14-35 days prior to Day 1	Pre-dose  ( $\leq 3$ days prior to Day 1) (In-clinic)	Day 1  (In-clinic: Pre-Dose 1)	Day 1  (In-clinic: Dosing & Post-Dose 1)	Day 1  (In-clinic: Dosing & Post Dose 2)	Days 2-6 (At-home)	Day 7  (-1 day) (In-clinic)	Days 8-13 (At-home)	Day 14  ( $\pm 1$ day) / Early Termination  (In-clinic)	Days 15-20 (At-home)	Day 21  ( $\pm 1$ day) (In-clinic)
Orthostatic VS 	X (3 times, 15-20 min apart)	X		X (2-4 hours post 1 st dose)	X (2-4 hours post 2 nd dose)		X (2-4 hours post dose)		X (2-4 hours post dose)		X
Clinical Chemistry	X	X			X 		X 		X 		X
Hematology	X	X			X 		X 		X 		X
Urinalysis 	X	X			X 		X 		X 		X
Biomarker panel for renal tubular injury		X			X 		X 		X 		X
Pregnancy Test	X 	X 					X 		X 		X 
HIV, CCI HBsAg, HCVAb	X										
TSH – FSH (optional for females only; if needed)	X										

Commercially Confidential Information

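### Inclusion criterion 9 sets the postmenopausal FSH threshold at 38 IU/mL (38,000 IU/L), a unit that appears wrong by a factor of 1000; confirm it and correct it in all three places

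*Protocol*

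**What the plan says.** The criterion is worded as a requirement. It opens with "Postmenopausal women must have had", asks for at least 365 days of spontaneous amenorrhea and a documented FSH of at least 38, and continues "IU/mL, prior to screening. If needed, per Investigator's judgment, FSH level can be performed at Screening" (protocol Section 4.1, criterion 9). The same number and unit stand in criterion 9 of the Synopsis and in footnote [1] to the Endocrinology panel of Appendix B.

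Three other provisions bear on how strictly it applies:

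- Section 4.1 introduces its list with "Subjects who meet all of the following criteria will be eligible to participate in the study".
- Section 6 states that "Protocol waivers or exemptions are not allowed".
- The Schedule of Assessments (Appendix A, Table 2) lists the test at Screening as "FSH (optional for females only; if needed", with no unit.

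The neighbouring criteria cover the other reproductive classes. Criterion 8 sets pregnancy testing for women of childbearing potential, criterion 10 sets the documentation for surgically sterile women, and criterion 11 sets contraception for subjects with reproductive potential. Neither document gives an FSH value in mIU/mL or IU/L, and neither gives an FSH reference range.

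**The concern.** The threshold helps decide how a woman is classified on entry. That classification governs whether she needs repeated pregnancy tests and two methods of contraception and, on a strict reading, whether she may enter at all. The trial enrols up to age 75, so naturally postmenopausal women are to be expected among the subjects.

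A threshold 1000 times too high cannot do this job. A site that follows the text exactly has three options for a naturally postmenopausal woman: exclude her, enrol her and record an eligibility deviation, or treat her as of childbearing potential. A site that reads the number in the unit on its laboratory report does something different. With up to 15 sites, the same woman could be handled in several ways without anyone having decided which was meant. The sentence allowing FSH to be measured at Screening does not help, because it concerns when the value may be obtained and leaves the threshold unchanged.

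**Working it through.** No figure in the plan is derived from this threshold, so there is nothing to reproduce. The check is a unit conversion followed by a comparison with an assumed range.

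**Inputs from the protocol**

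- Threshold: 38 IU/mL (Synopsis criterion 9; Section 4.1 criterion 9; Appendix B footnote [1]).
- Every inclusion criterion must be met (Section 4.1), and waivers are not allowed (Section 6).

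**Input assumed**

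- Postmenopausal FSH of 20 to 300 IU/L. The documents give no range. This one is deliberately wide, and the conclusion is checked at both ends.

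**Step 1: convert the threshold.** 1 mL is 1/1000 L, so 38 IU/mL × 1000 mL/L = 38,000 IU/L. Because 1 IU/L = 1 mIU/mL, this is also 38,000 mIU/mL. The conversion is exact.

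**Step 2: convert the assumed range to the printed unit.** 20 IU/L ÷ 1000 = 0.02 IU/mL, and 300 IU/L ÷ 1000 = 0.3 IU/mL.

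**Step 3: compare.**

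| Assumed FSH | In IU/mL | Threshold ÷ value | Meets 38 IU/mL? | Meets 38 IU/L? |
|---|---|---|---|---|
| 20 IU/L | 0.02 | 38,000 / 20 = 1900 | No | No |
| 40 IU/L | 0.04 | 38,000 / 40 = 950 | No | Yes |
| 100 IU/L | 0.1 | 38,000 / 100 = 380 | No | Yes |
| 150 IU/L | 0.15 | 38,000 / 150 = 253 | No | Yes |
| 300 IU/L | 0.3 | 38,000 / 300 = 127 | No | Yes |

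No value in the range meets the printed threshold. For one to do so, the top of the range would have to be about 127 times higher than assumed.

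**Step 4: test the alternative unit.** Read as 38 IU/L, the threshold is 0.038 IU/mL. It lies between 20 and 300 IU/L and separates lower from higher values, as a menopausal cut-off should. The printed and alternative readings differ by 38,000 / 38 = 1000.

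**Step 5: check for an extraction error.** The same unit appears in three separate parts of the protocol, which makes a slip in reading the PDF unlikely.

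**The case against.** There is a good case that this matters little.

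- **The documents do not contradict themselves.** The three statements agree, and the error shows only against the FSH scale, which has to be assumed. This is correct. The margin is so large, however, that the choice of range does not affect the answer.
- **Criteria 8 to 11 can be read as a classification.** A woman without a qualifying FSH is then not confirmed under criterion 9 but can be handled under criteria 8 and 11, with pregnancy tests and contraception. A woman with a documented hysterectomy, ovariectomy or tubal ligation has criterion 10. A reader might infer that no postmenopausal woman can enter the trial; these routes mean the documents do not support that. The route through criteria 8 and 11 is arguable rather than explicit, because criterion 9 is worded as mandatory for postmenopausal women.
- **Sites would probably read the figure as mIU/mL.** The test is optional, its timing is left to the investigator's judgment, and Section 7.11 refers laboratory conduct to a manual that is not among the documents. This limits the practical effect but leaves the printed text wrong.
- **The analysis is largely insulated.** Under SAP Section 5 the Safety Population needs only one dose. The FAS needs, in addition, a TETRAS-PS total score at Day 7, Day 14 or early termination. Neither depends on eligibility deviations, so this stands in full.

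A reader might also infer that a particular number of the roughly 30 subjects is affected, or that they would drop out of the Per-Protocol Population. The documents support neither. They give no sex or age distribution. The Per-Protocol Population excludes subjects with a major deviation, while the shell for SAP Listing 16.2.2.3 allows both major and minor and nothing grades this one.

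**Conclusion.** The point holds as a unit error in a mandatory eligibility threshold. As printed, the threshold is 38,000 IU/L. On an assumed postmenopausal range of 20 to 300 IU/L, it is 127 to 1900 times any value, and no naturally postmenopausal woman could meet it. The factor of 1000 is exact if mIU/mL or IU/L was intended. That intention is an inference from where the number 38 falls in the assumed range, and the sponsor must confirm it.

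The consequence is limited to how naturally postmenopausal women are admitted and classified, and how consistently sites do so. The visible traces in the reporting would be the unmet criteria in SAP Listing 16.2.2.2, any deviations recorded, and the childbearing-potential rows of SAP Table 14.1.2.1. The primary safety analysis and the FAS efficacy analyses do not depend on the threshold, so the likely effect on the results is small. The text should still be corrected, because sites decide eligibility from it and neither document gives the threshold in another unit.

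**What to change.** 1. Confirm the unit in which the central laboratory reports FSH.
2. Correct the unit in Synopsis criterion 9, Section 4.1 criterion 9 and Appendix B footnote [1] together: to mIU/mL, equivalently IU/L, if that is confirmed.
3. If enrolment is closed, record the intended unit in a dated note before eligibility deviations are graded, so that criterion 9 is judged in the same way for every woman.

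No SAP text needs editing. A reader might expect Listing 16.2.2.1 to carry the error, but its shell spells out only inclusion criterion 1 and uses placeholders for the rest; the programmed listing should simply take up the corrected criterion.

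The cost is one unit changed in three places by administrative amendment, or a short note if enrolment is closed. No endpoint, sample size or analysis method changes.

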#### **4.2 Exclusion Criteria**

Subjects who meet any of the following criteria will be excluded from participation in the study:

1. Prior or ongoing medical condition or any abnormal finding on the Screening visit physical exam, ECG, laboratory testing that, in the Investigator's opinion, could adversely affect the safety of the subject or the conduct of the study assessments.
2. Any neurological abnormality other than ET upon neurological exam, including dystonia, ataxia, or any other neurodegenerative disease, including multiple sclerosis or Parkinson's disease.
3. Commercially Confidential Information
4. Significant cognitive impairment or dementia that, in the opinion of the Investigator, would interfere with participation in the study.
5. Commercially Confidential Information
6. Commercially Confidential Information
7. An unstable thyroid condition that, per the Investigator's judgment based on medically significant abnormality of thyroid function testing at Screening. Note: an abnormal TSH level at Screening can be followed by reflex testing of thyroid hormones (T3, T4), if needed, per the Investigator's judgment.
8. History of, or evidence of psychogenic tremor at Screening.
9. Commercially Confidential Information
10. Commercially Confidential Information

11. History of anaphylaxis or hypersensitivity reactions to any of CAD-1883 excipients.
12. Alkaline phosphatase, aspartate aminotransferase (AST), and/or alanine aminotransferase (ALT) level  $>2.5 \times$  upper limit of normal (ULN) at Screening and/or at Baseline/Pre-dose.
13. Serum creatinine  $>120 \mu\text{mol/L}$  and/or creatinine clearance  $<60 \text{ mL/min}$  (according to Cockcroft-Gault formula) at Screening and/or at Baseline/Pre-dose.
14. Total bilirubin  $>2.0 \times$  ULN at Screening and/or at Baseline/Pre-dose. Note: isolated bilirubin  $>2.0 \times$  ULN is acceptable if bilirubin is fractionated and direct bilirubin is  $<35\%$ .
15. Exclusionary ECG abnormalities:
  - a. History of Long QT syndrome and/or QTcF (Fridericia's correction) interval  $>450 \text{ msec}$  (males) or  $>470 \text{ msec}$  (females) per 12-lead ECG done at Screening.

Commercially Confidential Information

16. Commercially Confidential Information

17. History of Alcohol Use Disorder per Diagnostic Statistical Manual of Mental Disorders, Fifth Edition (DSM-V) criteria.
18. History of human immunodeficiency virus (HIV) infection or positive screening result for: HIV 1 or 2 antibodies, hepatitis B surface antigen (HBsAg), or hepatitis C virus antibody (HCVAb).

Commercially Confidential Information

19. Has a diagnosis of epilepsy or any history of seizure as an adult, head trauma, stroke, transient ischemic attack within 1 year prior to Screening, unexplained loss of consciousness within 1 year prior to Screening, or any lifetime history of asymptomatic or symptomatic orthostatic hypotension (e.g., postural syncope).
20. History of unstable angina, myocardial infarction, chronic heart failure (New York Heart Association Class 3 or 4), or clinically significant conduction abnormalities (e.g., unstable atrial fibrillation) within 1 year prior to screening.

21. Commercially Confidential Information
22. Commercially Confidential Information
23. Commercially Confidential Information
24. Commercially Confidential Information
25. Any major psychiatric disorder that is uncontrolled (for the past 90 days) that, per the Investigator's judgment, can interfere with any of the study procedures.
26. Subject has cancer, except for the following: basal cell carcinoma or successfully treated squamous cell carcinoma of the skin; cervical carcinoma in situ; prostatic carcinoma in situ; or other malignancies curatively treated and with no evidence of disease recurrence for at least 3 years.
27. Commercially Confidential Information
28. Commercially Confidential Information
29. Commercially Confidential Information
30. Subjects with scheduled surgeries during the study period.

